The biopsy results can be classified into three categories: positive results, including malignant or benign lesions confirmed by a follow-up period, or negative results, including [18] intermediate histological samples, such as chronic inflammation, organizing pneumonia, or atypical cells without sufficient features to ascertain malignancy; or [22] indeterminate samples, such as normal lung tissue or insufficient sample size [6]. The tissue samples that produce intermediate and indeterminate samples should be further evaluated according to recommended guidelines for the management of pulmonary nodules.

In this study, the diagnostic yield of the bronchoscopic procedure (Robotic-guided TBNA or Robotic-nCLE-guided TBNA) will be defined as the proportion of patients in whom the bronchoscopic procedure yield a definitive diagnosis out of the total number of patients that have received the diagnostic procedure. This value is affected by the lesions' sizes, locations, and the existence of a bronchus sign or an airway leading directly into the lesion [23].

Primary objective:

To compare the first-pass diagnostic yield of the sequential needle passes (ROSE) between the Robotic-nCLE-guided TBNA arm and the Robotic-guided arm in PPNs.

Secondary objectives:

[figure not shown]
1. To compare the per-patient diagnostic yield (cumulative pass diagnostic yield: cumulative number of passes until five cumulated passes) of Robotic-nCLE-guided TBNA to that of Robotic-guided TBNA in PPNs.
2. To compare the proportion of patients with lung cancer treatment in the Robotic-nCLE-guided TBNA arm to that of the Robotic-guided TBNA arm in PPNs.
3. To compare the proportion of patients with follow-up (video-assisted thoracoscopic surgery (VATS) or TTNA or TBNA procedures in the Robotic-nCLE-guided TBNA arm to that of the Robotic-guided TBNA arm in PPNs.
4. To compare the number of passes needed to obtain a final diagnosis of Robotic-nCLE-guided TBNA to that of Robotic-guided TBNA in PPNs.
5. To assess the diagnostic performance (sensitivity, specificity, PPV, NPV, accuracy) of the sequential cumulative nCLE passes and the sequential cumulative ROSE passes using the final diagnosis as a reference.
6. To assess the feasibility by obtaining adequate CLE video footage in >80% of the PPN punctures.
7. To assess the safety of nCLE imaging, as defined by:

- a. The number and frequency of all AE/SAE from the start of the procedure until end of 12-month follow-up

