2. First-two-passes cumulative diagnostic yield is calculated as the proportion of patients for which first-two-passes cumulative TBNA pass during the bronchoscopic procedure yielded a definitive diagnosis out of the total number of patients that have received a diagnostic procedure.
3. First-three-passes cumulative diagnostic yield is calculated as the proportion of patients for which first-three-passes cumulative TBNA pass during the bronchoscopic procedure yielded a definitive diagnosis out of the total number of patients that have received a diagnostic procedure.
4. Etc.... until the fifth pass.

The number of patients has been calculated to demonstrate an increase of the TBNA first-pass diagnostic yield by 20%, from 70% to 90%, between the Robotic-guided TBNA and the Robotic-nCLE-guided TBNA, with a statistical power of 80% with a 2-sided significance level of 0.05. A group size of 59 patients per arm has been derived. By including 59 patients in each arm, we expect to image at least 29 malignant nodules (prevalence of 0.5) in each arm.

The study will enroll 118 consecutive patients randomly assigned 1:1 to Robotic-guided TBNA arm or Robotic-nCLE-guided TBNA arm.

5. Treatment of Subjects

Investigational product/treatment

In recent years, confocal laser endomicroscopy (CLE) has emerged as a novel technique that enables *in vivo* microscopic analysis during ongoing endoscopy [24]. CLE is based on tissue illumination with a low-power laser with subsequent detection of the fluorescence light reflected from the tissue. It is a contrast-based technique, the most widely used agent being the intravenously administered fluorescein. The probe of the endomicroscopy system consists of a flexible catheter probe representing a bundle of optical fibers linked to a micro-objective, a laser scanning unit, and the control and acquisition software (Cellvizio® I.V.E system, Mauna Kea Technologies, France). The principle of the technique is based on a laser beam of the defined wavelength being focused towards the targeted tissue, and the recaptured signal is displayed as 'optical biopsies' in a single horizontal plane.

[figure not shown]

Figure 1: A- Locking of the CLE probe to the aspiration needle. B- CLE probe inside endosonography needle. C- Endosonography images of n-CLE measurements (white arrow) inside a lymph node (LN) (Wijmans/Annema et al. [10]).

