Suppose a patient suspected of lung cancer has a negative result of the bronchoscopic procedure. In that case, a surgical procedure (mediastinoscopy or lobectomy/pneumectomy with lymph node dissection) could follow to obtain tissue. This surgical procedure will be performed regardless of the result of nCLE imaging. If a surgical procedure is indicated, we will collect the histological images to compare with nCLE imaging. This study will not interfere with the standard cytology or the standard histology process. Digital copies of the cytological and histological slides of the measured nodules will be obtained and compared with the frames of the nCLE sequences.

Final Diagnosis or Definitive Diagnosis

For this 12-month analysis, pathology results of Robotic-aided biopsy samples that will be diagnostic of a non-malignant condition or indeterminate will be referred to as negative for malignancy or negative for brevity. Follow-up will be conducted to determine the final diagnosis (malignant or non-malignant). All cases will be followed according to the practitioner's judgment and standard of care testing (e.g., surgical tissue biopsy, repeat Robotic, CT-guided transthoracic needle biopsy or aspiration (TTNA), serial CT imaging, and lung health visits). Cases with subsequent diagnostic tests confirming a non-malignant diagnosis or without lesion progression on radiographic follow-up will be considered true-negative at 12 months, consistent with prior Robotic studies. If the follow-up diagnostics reveal malignancy or lesion growth on repeat imaging with appropriate follow-up diagnostic testing, this will be considered a false-negative. The following will also be regarded as false-negative: death due to lung cancer within 12 months; treatment without a confirmed diagnosis; and new diagnosis of cancer in the lung from any site (including non-index lesions or lymph nodes diagnosed as malignant by linear bronchoscopy during or after the index procedure).

Twelve-month diagnostic yield will be calculated per subject as the rate of true-positives (for malignancy) plus true negatives (for malignancy) of all subjects with attempted lung lesion biopsies.

Adverse Events

Definitions

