- Accuracy: Probability that a Robotic-guided biopsy gives correct prediction among the total number of cases examined: $= (a + d)/(a + b + c + d)$

Patient diagnostic and management analysis:

Intermediate and final diagnosis and management recommendation proportion differences for the two patient populations (Robotic-guided TBNA arm and Robotic-nCLE-guided TBNA arm) will be compared using a chi-square test. Intermediate and final diagnosis and management recommendation proportions will also be compared for the two patient populations. Differences between Robotic-guided TBNA and Robotic-nCLE-guided TBNA arms regarding the specific diagnostic and management categories will be compared using McNemar's test both at the intermediate diagnosis and the final diagnosis stage.

Feasibility statistical analysis:

The feasibility of needle-based lung cancer diagnosis will be assessed by investigating the following items:

- Assessing nCLE-image quality
- Assessing the feasibility of the integrated needle/Cellvizio® I.V.E Confocal Miniprobe™.

The imaging feasibility yield for the Robotic-nCLE-guided TBNA procedure is defined as the proportion of patients in whom procedure will yield at least good nCLE image quality out of the total number of patients that will receive that procedure.

The mechanical feasibility yield for the Robotic-nCLE-guided TBNA procedure is defined as the proportion of patients for whom Robotic-nCLE-guided TBNA procedure will be possible mechanically (meaning that the nCLE probe will be guided to the nodule successfully) out of the total number of patients that will receive that procedure.

Safety:

The safety will be assessed by carefully monitoring adverse events related to both procedures. Serious adverse event rates will be calculated by dividing the number of events for each procedure divided by the total number of procedures for each arm.

Reproducibility:

To assess the reproducibility of bronchoscopy guided nCLE:

- Estimating the reproducibility of nCLE criteria will be evaluated by calculating the inter-observer agreement of nCLE criteria between 3 readers (Fleiss Kappa).

In Wijmans et al. [10], three nCLE characteristics for the detection of malignancy were identified in different subtypes of lung tumors and metastatic lymph nodes:

- 1) dark enlarged pleomorphic cells;
- 2) dark cell clusters consisting of overlapping cell structures ('dark clumps'); and

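### The twelve-month diagnostic yield is an accuracy rate: it generally credits an indeterminate sample as a success when the nodule proves benign at 12 months

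*Combined protocol and SAP*

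**What the plan says.** The rule is in section 5, under Final Diagnosis or Definitive Diagnosis, in three steps.

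- Biopsy results that are "diagnostic of a non-malignant condition or indeterminate will be referred to as negative for malignancy or negative for brevity" form one group.
- Cases "without lesion progression on radiographic follow-up will be considered true-negative at 12 months", and so will cases in which later tests confirm a non-malignant diagnosis.
- The yield is then defined: "Twelve-month diagnostic yield will be calculated per subject as the rate of true-positives (for malignancy) plus true negatives (for malignancy) of all subjects" with an attempted biopsy.

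The same paragraph lists exceptions that score as false-negative. They include lung cancer death within 12 months, treatment given without a confirmed diagnosis, and a new cancer in the lung from any site, non-index lesions included.

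Other sections bear on this rule:

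- The background, just before the objectives, separates positive biopsy results from intermediate samples (chronic inflammation, organizing pneumonia, atypical cells) and from "indeterminate samples, such as normal lung tissue or insufficient sample size". It defines yield as the share of patients in whom the procedure gives a definitive diagnosis.
- Section 4, Sample size calculation, treats a TBNA pass as non-diagnostic if further passes or tests are needed to reach the diagnosis. It also gives the planned case mix: "we expect to image at least 29 malignant nodules (prevalence of 0.5) in each arm".
- Section 7 defines per-patient yield as the background does. Separately it defines accuracy, (a + d)/(a + b + c + d), as the "Probability that a Robotic-guided biopsy gives correct prediction among the total number of cases examined".
- Section 8 words the first-pass (primary) and per-patient (secondary) yields in the same way: the pass or the procedure must give a definitive diagnosis.

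**The concern.** Taken together, the three steps mean that, for a benign nodule, what the needle brought back hardly matters. Normal lung, too little material and a specific benign diagnosis all end as true negatives, and all count as yield. The word negative also changes meaning. In the background it marks a result that is not a positive (malignant or confirmed benign) finding. In section 5 it means only that no malignancy was reported.

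This bears on the trial's own rationale. The Summary argues that without confirmation of needle position, a biopsy showing no tumor cells is often regarded as non-diagnostic, and that nCLE may reduce such biopsies. A measure that scores hits and misses alike in benign nodules cannot register that part of the benefit. The published twelve-month figure would be too high as a statement of yield in both arms, and a descriptive contrast between arms could be compressed.

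The section heading treats final and definitive diagnosis as one thing, and definitive diagnosis is the term on which the first-pass and per-patient yields rest. The plan does not say whether the section 5 rule is meant to reach those endpoints.

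**Working it through.** **The plan's own figure.** Inputs from section 4: 70% v 90% first-pass yield, two-sided 0.05, power 80%. With unpooled variance,

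n = (1.960 + 0.842)² × (0.7×0.3 + 0.9×0.1) / 0.2² = 7.851 × 0.30 / 0.04 = 58.9, so 59 per arm.

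This matches the plan. Exact power at 59 per arm is 80.5% with the uncorrected chi-square test, and 80.0% if Fisher's test replaces it when an observed cell is below 5. The sample size rests on first-pass yield, not on the twelve-month figure. Expected malignant nodules per arm: 59 × 0.5 = 29.5.

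**The two measures as formulas.** Let prev be the prevalence of malignancy. Let h be the share of malignant nodules, and b the share of benign nodules, correctly diagnosed by the index sample. Assume no false positives and, for now, no false-negative exceptions among benign nodules.

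- Strict yield = prev × h + (1 − prev) × b
- Section 5 twelve-month yield = prev × h + (1 − prev)

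The second does not contain b. Its arm difference is prev × (h₁ − h₀). The part it drops is (1 − prev) × (b₁ − b₀).

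**A procedure that never samples the nodule** (h = b = 0). Strict yield is 0%. The section 5 yield is 1 − 0.5 = 50% at the plan's prevalence. If prevalence were 0.3 to 0.7 (assumed range), it would be 70% to 30%. These are upper bounds, because the false-negative exceptions can remove some benign nodules from the true negatives.

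**Illustration with equal gain.** The plan gives no arm rates for the whole procedure and none by malignancy status. Borrow 70% and 90% and apply them to malignant and benign nodules alike:

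| Prevalence | Control | nCLE | Difference |
|---|---|---|---|
| 0.3 | 0.3×0.7 + 0.7 = 91% | 0.3×0.9 + 0.7 = 97% | 6 points |
| 0.5 | 0.5×0.7 + 0.5 = 85% | 0.5×0.9 + 0.5 = 95% | 10 points |
| 0.7 | 0.7×0.7 + 0.3 = 79% | 0.7×0.9 + 0.3 = 93% | 14 points |

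**Illustration with unequal gain.** Hold prevalence at 0.5 and strict yield at 70% v 90%, and vary where the gain falls:

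| Malignant, control to nCLE | Benign, control to nCLE | Section 5 yield | Difference |
|---|---|---|---|
| 50% to 90% | 90% to 90% | 75% v 95% | 20 points |
| 60% to 90% | 80% to 90% | 80% v 95% | 15 points |
| 70% to 90% | 70% to 90% | 85% v 95% | 10 points |
| 80% to 95% | 60% to 85% | 90% v 97.5% | 7.5 points |
| 90% to 90% | 50% to 90% | 95% v 95% | 0 points |

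Provided nCLE lowers the hit rate in neither group, the section 5 difference lies between 0 and 20 points when the strict difference is 20.

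**The case against.** The strongest reply is that the plan never compares arms on this figure. It appears only in section 5. It is absent from the objectives and from section 8, and section 7 gives it no test. The planned yield comparisons use other wording, and section 8 already has yield and accuracy compared for each method. The section 4 rule on additional tests scores a single pass, whereas section 5 scores a subject at 12 months. The background's positive class itself admits benign lesions confirmed by follow-up, and section 5 describes its true-negative rule as in line with earlier studies.

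Most of this stands and limits the point. A reader might infer that the trial is underpowered: for 85% v 95% at 59 per arm, exact power is 45% with the chi-square test, or 32% with the switch to Fisher's test. But that is the power of a test the plan does not contain, computed from first-pass rates that the plan does not assign to the twelve-month measure. A reader might also infer that the arm difference is always halved. That needs both prevalence 0.5 and an equal gain in malignant and benign nodules, and the plan supplies no yield by malignancy status. Nor does every indeterminate sample from a benign nodule succeed, given the exceptions. Lesions that cannot be localized may also leave under the intra-operative criteria in section 4.

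What the reply does not remove is the conflict in the text. One term, diagnostic yield, has two incompatible definitions, and the looser one sits under the heading that defines the term used by the primary endpoint. Confirming a benign lesion by follow-up differs from crediting a sample that the background itself calls indeterminate. Agreement with earlier studies is a reason to report the figure, not to call it yield.

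**Conclusion.** The concern holds as a defect of definition. The section 5 rate has the form of section 7's accuracy, generally counts indeterminate samples from benign nodules as diagnosed, and conflicts with the yield definitions in the background and in sections 7 and 8. At the plan's prevalence of 0.5, up to 50% is attainable without sampling any nodule, and the measure is blind to fewer non-diagnostic biopsies in benign nodules.

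The effect on the arm difference is conditional. The 10 points in place of 20 is an illustration resting on borrowed first-pass rates, prevalence 0.5 and equal gains; the range with strict yield fixed is 0 to 20 points. The documents do not show that the 59 per arm, or its stated power for the first-pass endpoint, is wrong on this account. The primary and per-patient yields would be affected only if an analyst read definitive diagnosis through the section 5 rule, which the shared heading allows but no sentence instructs.

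**What to change.** In section 5, rename the rate of true positives plus true negatives as twelve-month accuracy, to match section 7. Then state once, for the first-pass, per-patient and twelve-month yields alike, that a subject counts as diagnosed only if the index sample itself (for first-pass yield, the first-pass sample) gave a malignant or a specific benign diagnosis that is not contradicted at 12 months. The background's indeterminate and intermediate classes, both of which it sets among negative results, then count as non-diagnostic whatever follow-up shows. List in advance which pathology results qualify as specific benign, since the plan does not define this. Report accuracy beside the strict yield so that comparison with earlier studies remains possible.

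The cost is a change of wording, one extra tabulation, and coding of pathology results into the background's categories. Section 6 already collects the ROSE and pathology diagnoses but does not list those categories as a field. No extra patients, samples or visits are needed. The reported yield will be lower than under the present rule.

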In the present study, we aim to compare the diagnostic yield of Robotic-nCLE-guided TBNA for lung cancer diagnosis to conventional Robotic-guided TBNA using the final diagnosis (histology or follow-up) as the standard reference. Furthermore, we will create an image atlas of the characteristics of nCLE-images in PPNs. Also, we aim to describe tumor types based on in-vivo characteristics. Improved characterization of distal lung lesions might lead to improved and quicker cancer diagnosis and patient care.

Background: nCLE imaging of PPNs under bronchoscopic guidance is feasible and safe.

Primary objective:

To compare the first-pass diagnostic yield of the sequential needle passes (ROSE) between the Robotic-nCLE-guided TBNA arm and the Robotic- guided TBNA arm in PPNs.

Primary endpoint:

Increase of the first-pass diagnostic yield by 20%, from 70% to 90%, between Robotic-nCLE-guided TBNA arm and the Robotic- guided TBNA arm in PPNs.

Secondary objectives:

1. To compare the per-patient diagnostic yield (cumulative pass diagnostic yield: cumulative number of passes until five cumulated passes) of Robotic-nCLE-guided TBNA arm to that of Robotic-guided TBNA arm in PPNs.
2. To compare the proportion of patients with lung cancer treatment in the Robotic-nCLE-guided TBNA arm to that of the Robotic-guided TBNA arm in PPNs.
3. To compare the proportion of patients with follow-up (video-assisted thoracoscopic surgery (VATS) or TTNA or TBNA procedures) in the Robotic-nCLE-guided TBNA arm to that of the Robotic-guided TBNA arm in PPNs.
4. To compare the number of passes needed to obtain a final diagnosis of Robotic-nCLE-guided TBNA to that of Robotic-guided TBNA in PPNs.
5. To assess the diagnostic performance (sensitivity, specificity, PPV, NPV, accuracy) of the sequential cumulative nCLE passes and the sequential cumulative ROSE passes using the final diagnosis as a reference.
6. Feasibility: obtain adequate CLE video footage in >80% of the PPN punctures.
7. To assess the safety of nCLE imaging, as defined by:
 - a. The number and frequency of all AE/SAE from the start of the procedure until end of 12-month follow-up;
 - b. The number and frequency of nCLE procedure-related AE/SAE from the start of the procedure until end of 12-month follow-up.
8. To assess the reproducibility of nCLE criteria with regard to the reference standard. Three nCLE characteristics for the detection of malignancy were identified during Wijmans et al. study [10]:

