- b. The number and frequency of nCLE procedure-related AE/SAE from the start of the procedure until end of 12-month follow-up
- 8. To assess the reproducibility of nCLE criteria to the reference standard. Three nCLE characteristics for the detection of malignancy were identified during Wijmans et al. study [10]:
 - a. Dark enlarged pleomorphic cells;
 - b. Dark cell clusters consist of overlapping cell structures ('dark clumps') and
 - c. Continuous movement of the cells in one direction ('directional streaming').
- 9. To create an nCLE image atlas for malignant characteristics in PPNs.

3. Study Design

This is a randomized, controlled, interventional, comparative prospective multi-center study. In total, a maximum of 118 consecutive patients with a (suspected) PPN who are referred for a diagnostic bronchoscopic (Robotic-guided TBNA) procedure will be considered for enrollment. The estimated duration of the study is 24 months. Patients will be consecutively recruited and randomly assigned to undergo Robotic-guided TBNA (n=59) or Robotic-nCLE-guided TBNA (n=59).

Only patients in the nCLE arm will receive intravenously administered fluorescein before the start of the Robotic procedure. During the nCLE procedure, an 18G needle enters the targeted tissue, followed by an nCLE AQ-Flex™ 19N Confocal Miniprobe™ (Mauna Kea Technologies, France) through the biopsy needle, to obtain real-time imaging. nCLE imaging will be performed in the PPNs with a total estimated time for research measurements of 10 minutes. nCLE imaging will be performed for each sequential TBNA pass/sampling within the lung nodule lesion and each TBNA path cytopathological result will be correlated with the nCLE sequence acquired for that TBNA pass. TBNA sampling will end when sufficient diagnostic material will be found with ROSE (as assessed by the cytopathologist) or when the physician performing the procedure judges that the number of samplings/passes is adequate. ROSE will be performed by a cytopathologist.

4. Study Population

Population (base)

Patients with a PPN referred for diagnostic bronchoscopic/endosonographic workup tissue sampling based on standard (PET-) CT imaging

Inclusion criteria

To be eligible to participate in this study, a study subject must meet all of the following criteria:

- ≥ 21 years of age
- Suspected PPN
- Nodule size in CT between 8 mm and 30 mm (largest dimension)

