AEs and SAEs recording and reporting

Upon identification of an AE or SAE, the site investigator will utilize the above definitions to properly classify attribution and expectedness of the event. All SAEs must be recorded for each event.

All AEs and SAEs will be recorded in the “AE case report forms” (CRF) and in progress reports with details about the grade and attribution of each episode, action taken with respect to the study drug, and the patient’s outcome will be recorded in the CRF. All events will be recorded on case report forms for the duration of the study until they resolve.

The investigator/ site is responsible to report all SAEs that occur on or after the first day of study treatment to the sponsor within 24 hours of becoming aware of the event. It may be necessary to submit a final SAE report if the initial report did not have the complete information. All SAEs will be recorded on the FDA MedWatch form 3500a. The attribution and expectedness must be recorded on the MedWatch form. If this information is not available at the time of initial reporting, a final report must be documented with attribution and expectedness. It may be necessary to submit follow up reports to the Sponsor should the event require further investigation. All subsequent SAEs must be recorded for up to 5 after the last treatment. Each investigator is responsible to report all AEs/SAEs to their local IRB following guidelines set by that IRB.

Follow-up of adverse events

After the initial AE/SAE report, the Investigator is required to follow-up on each subject who experienced the AE at subsequent visits or contacts.

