All patients will be evaluated for adverse events (AEs) and serious adverse events (SAEs) at the procedure day, 7 days, and 30 days post-procedure. On the day of the procedure the principal investigator will evaluate possible signs and symptoms such as shortness of breath, chest pain, dizziness, low blood oxygen saturation ($\geq 90\%$), hemoptysis (cough bright red blood) and fever ($> 37.3\text{ C}$). At Day 7(post procedure), a study team will contact the patient by the phone and ask about any symptoms of shortness of breath, chest pain, cough with yellow or greenish sputum, hemoptysis (cough bright red blood) and fever. At Day 30, the study team will review patient's medical records and collect data of medications, doctor visits (primary care and specialist visits), procedures and other medical records information. In addition, patients will be instructed to call in with concerns and/or present to the research staff or Principal Investigator. . The study staff will be recording and reporting in the electronic medical record all the adverse events with an attribution of possibly, probably, or definitely related to the study intervention.

Depending on the event, follow up may require additional tests or medical procedures as indicated and/or referral to the general physician or a medical specialist.

Stopping rules based on safety considerations

Investigators will be responsible for data and safety monitoring for this trial. Investigators will discuss with the statistician and/or the study Sponsor if higher than expected rate of adverse events of unacceptable grades are documented. If the rate is more than 10 % of the patient with bleeding, more than 5% with pneumothorax or respiratory failure and 1 patient with anaphylaxis, the principal investigator will consider stopping the study. Statistician and/or Sponsor, after discussion with the Investigator, may recommend to close the study to IRB if the rate of study related adverse events is between the parameters mentioned previously.

6. Data Collection

Subject demographics

- Age
- Sex
- Ethnicity
- Race

Subject medical history and baseline status

- Prior invasive lung procedures and surgeries
- Lung function and diffusing capacity
- Antithrombotic medication current and prior status, including duration of any discontinuation
- Subject risk factors
- Pre-procedure probability of malignancy

Lesion characteristics

- Size
- Location
- Presence of bronchus sign on computerized tomography (CT)

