- Twelve months follow-up data: repeat diagnostic procedures or new diagnoses on any lung nodule evaluated during the initial bronchoscopic index procedure, as well as healthcare utilization since the bronchoscopic index procedure (including healthcare visits, repeat bronchoscopic procedures, transthoracic biopsy, bronchoscopy, chemotherapy, brachytherapy, radiation therapy, surgical resection, and lymph node dissection).

nCLE image quality:

nCLE image quality for each nodule will be rated by the interventional pulmonologist as:

- **Very poor:** impossibility to observe any structure or criteria
- **Poor:** The observed criteria and structures are hardly recognisable and interpretable
- **Moderate:** Structures and criteria are recognisable and interpretable with close attention, but confidence in the interpretation remains low (may require replaying the sequence frame by frame)
- **Good:** Image quality is sufficient to enable an easy structures and criteria observation and interpretation (may require replaying the sequence frame by frame)
- **Very good:** criteria and structures are recognisable and interpretable very easily

Diagnostic and Therapeutic Management

Lung cancer treatment options are the following:

- **Minimally invasive surgery.** Thoracic surgeons can use minimally invasive techniques when possible, including [video-assisted thoracoscopic surgery \(VATS\)](#) and [robotic surgery](#). Surgeons remove the smallest amount of lung tissue necessary through wedge resection, sleeve lobectomy, and bilobectomy.
- **Highly targeted radiation therapy.** Radiation oncologists have access to the latest technology to carefully shape and precisely deliver radiation to the target. Targeted treatment is available through [intensity-modulated radiation therapy \(IMRT\)](#), volumetric modulated arc therapy (VMAT), [image-guided radiation therapy \(IGRT\)](#), and [proton therapy](#). These techniques reduce the risk of side effects and improve outcomes.
- **Carefully selected systemic therapy.** Mayo Clinic oncologists have access to various systemic treatments, including [chemotherapy](#), targeted therapy, and immunotherapy. Systemic treatments are selected using many factors, including the genetic makeup of your cancer cells.

[figure not shown]

Figure 3: Randomized controlled study device with two arms: Robotic-guided TBNA and Robotic-nCLE-guided TBNA with the different steps

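### Safety objective 7 counts all AE/SAEs to 12 months, but dated AE evaluation ends at day 30 and one sentence names only related events: window and scope need aligning

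*Combined protocol and SAP*

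**What the plan says.** Objective 7, in the Summary and again in the full list of secondary objectives, has two parts. Part 7a is "The number and frequency of all AE/SAE from the start of the procedure until end of 12-month follow-up". Part 7b is "The number and frequency of nCLE procedure-related AE/SAE from the start of the procedure until end of 12-month follow-up".

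Section 5, Follow-up of adverse events, sets AE and SAE evaluation "at the procedure day, 7 days, and 30 days post-procedure". Day 7 is a telephone call about a short symptom list and day 30 is a medical-record review. Patients are also told to call in with concerns. The same paragraph has study staff "recording and reporting in the electronic medical record all the adverse events with an attribution of possibly, probably, or definitely related to the study intervention".

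Section 5, AEs and SAEs recording and reporting, puts all AEs and SAEs on the AE case report form and "in progress reports with details about the grade and attribution of each episode". It keeps events on the CRF throughout the study and until resolution. It also states: "All subsequent SAEs must be recorded for up to 5 after the last treatment".

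Section 6, Follow-up assessment, lists adverse events as a data item without a date. The one item there with a date begins "Twelve months follow-up data: repeat diagnostic procedures or new diagnoses on any lung nodule evaluated during the initial bronchoscopic index procedure" and goes on to healthcare utilization; it does not name adverse events.

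Section 7, Safety, defines SAE rates as events divided by procedures in each arm and gives no time window.

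**The concern.** The plan gives more than one answer to two basic questions: until when are events sought, and which events count?

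On the window, the objective runs to month 12 but the dated evaluations stop at day 30. Recording an event that has come to light is different from looking for events in every patient at set times. After day 30 the plan clearly provides for the first, but it does not schedule the second.

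On scope, objective 7a wants all events, while the medical-record sentence names only those possibly, probably or definitely related.

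Section 8, Safety, makes comparison with Robotic-guided TBNA a secondary goal. Only one arm receives fluorescein and the imaging probe, so the operator knows the assignment. If later events are found through contacts that vary from patient to patient, the 12-month frequency can be too low, and the shortfall need not be equal in the two arms. Two sites could each follow the text in good faith and return different safety data.

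**Working it through.** The plan states no figure to reproduce on this point. The check sets the provisions side by side, with one piece of calendar arithmetic.

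**Window**

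1. Objectives 7a and 7b: start of the procedure to the end of 12-month follow-up.
2. Dated AE/SAE evaluations (Section 5, Follow-up of adverse events): days 0, 7 and 30. No later date is given.
3. Calendar gap, taking 12 months as 365 days: 365 − 30 = 335 days without a dated AE evaluation.
4. CRF rule (Section 5, AEs and SAEs recording and reporting): events are recorded throughout the study. That subsection starts from the point at which an event has been identified. It extends recording past day 30 but sets no time at which events are to be sought.
5. Follow-up assessment (Section 6): AEs are listed, undated. Neighbouring items refer to the last visit, but no schedule of visits after day 30 is given. Section 5, Final Diagnosis or Definitive Diagnosis, leaves follow-up to the practitioner's judgment and standard of care, so the number of contacts can vary between patients. Objectives 2 and 3 compare later treatment and later procedures between the arms. If those differ, contact frequency can differ by arm too.
6. Twelve-month item (Section 6): repeat procedures, new diagnoses and healthcare utilization. AEs are not named.
7. SAE rates (Section 7, Safety): events ÷ procedures, per arm. The numerator depends on the window, which is not stated.

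Items 4 to 6 show that recording beyond day 30 is intended. None of them supplies a uniform evaluation between day 30 and month 12.

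**Which late events are exposed**

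The SAE definition in Section 5 includes events requiring hospitalization. Section 6 collects hospital and emergency care related to lung health since the index procedure, and healthcare utilization over twelve months. Late SAEs that lead to such care therefore have a planned route into the data in both arms. A late non-serious event that leads to no recorded health service has only an undated follow-up item or a patient's call. The gap lies mainly there.

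**Scope**

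1. Objective 7a: all AEs and SAEs.
2. AE definition (Section 5, Definitions): applies whether or not the event is thought to be related.
3. CRF rule: all AEs and SAEs, with attribution.
4. Attribution scale (Section 5): includes unlikely and unrelated categories, and its heading covers both nCLE and the standard robotic procedure.
5. Medical-record sentence: names "all the adverse events with an attribution of possibly, probably, or definitely related to the study intervention".

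Items 1 to 4 agree with one another. Item 5 does not fit them.

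**The case against.** The strongest reply is that the plan already records AEs beyond day 30. The CRF rule covers every AE and SAE during the study, adverse events appear under Follow-up assessment, and the health-service items would bring in most serious late events. The related-only sentence concerns the electronic medical record, does not contain the word only, and does not override the CRF rule. The listed possible AEs are also largely procedural, so much of what matters may occur before day 30.

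Most of this stands, and it rules out several stronger readings that a reader might infer:

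- That objective 7 cannot be delivered as written. The CRF rule and the Section 6 follow-up item contradict this. What is missing is a dated, uniform evaluation after day 30.
- That relatedness filtering would push the control-arm count towards zero. This requires the medical-record sentence to be read alone. The attribution heading in Section 5 includes the standard robotic procedure, and Section 7, Safety, covers events related to both procedures, so a control-arm pneumothorax or bleed can be attributed and counted.
- That 30/365 = 8.2% measures how many events would be caught. It is a share of calendar time, and the plan gives no distribution of event times.
- That the SAE limit of up to 5 is a third, conflicting window. The unit is absent from the text available, which may be a fault of text extraction or a redaction. It is a query and carries no weight here.

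The reply does not remove the mismatch between a 12-month objective and a schedule that ends at day 30. Nor does it reconcile the medical-record sentence with the all-event scope.

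**Conclusion.** The concern holds as an inconsistency of window and scope affecting one secondary objective. AE evaluation is dated only to day 30 of a 12-month safety objective, about 335 calendar days have no uniform ascertainment, and one sentence names a narrower set of events than the objective, the AE definition and the CRF rule.

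The consequence is a possible under-count of late events, mainly non-serious ones, in any frequency reported as 12-month, with possible unevenness between patients and arms. Neither the number missed nor a difference between arms can be derived from the documents. The primary endpoint, sample size, power and significance level are not affected.

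The conclusion assumes that 12 months is 365 days and that no later AE schedule stands in text that was unavailable, such as the missing figures. It should be corrected; it does not invalidate the trial.

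**What to change.** 1. Choose one window for objectives 7a and 7b. Either add AEs and SAEs explicitly to the 12-month data collection, asked in the same way in both arms, or restate both objectives as running to day 30.
2. State that same window for the SAE rates in Section 7, Safety.
3. Align the medical-record sentence in Section 5, Follow-up of adverse events, with the CRF rule: all AEs in both arms go on the CRF whatever their attribution, and attribution to nCLE or to the standard robotic procedure is a separate field.
4. As a query only, ask the sponsor for the unit that belongs after up to 5 in the SAE recording sentence, and check that it agrees with the chosen window.

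Restating to day 30 costs wording alone. Keeping 12 months adds a small amount of data collection. The plan describes twelve-month data items but does not specify a patient contact at that time, so the sponsor should say how the AE information will be obtained.
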